## 7.6 Secondary performance endpoint analyses

All secondary performance endpoint analyses will be performed on the ITT and PP populations. Results of statistical tests will be two-sided and given for information purpose only.

The secondary performance variables will be described by treatment group at each visit on raw values and on the changes / baseline D0.

The treatment groups will be compared at each post-baseline time using the same covariance model used to analyze the primary endpoint. The interaction Treatment x Baseline will be tested and removed from the model if not significant. If significant, the interaction will be kept in the model (a graphical representation of the interaction will be displayed) and the Treatment effect will be approximated by using the global average of observed D0 values (Note that in case of interaction, the Treatment effect cannot be properly interpreted). In addition, the distribution of the residuals of the analysis of variance will be tested: if the normality is not verified (Shapiro-Wilk test at the 1% threshold), the analysis will be performed on the ranks of the data (if analyses on ranks and on raw values lead to the same conclusions, only analysis on raw values will be given).

Depending on the distribution of the data (multinomial data such as global assessment of dry symptoms evaluations), a sensitivity analysis will be performed to compare both groups using a generalized linear model for multinomial data (SAS® Glimmix Procedure) with the value at baseline as covariate.

For the Ocular surface fluorescein staining test, the % of patients with a total score at 0 at D28 and D90 will be given with its 95% confidence interval.

Graphical representations by bar charts will be provided for dry eye symptoms and OSD-QoL dimension scores.

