7.6 Statistical Analysis

7.6.1 Methods of Analysis

Summaries for continuous variables will include the sample size (n), mean, standard deviation (SD), median, minimum, and maximum. Calculations will be based on the number of subjects (or eyes) with non-missing values for the study population being summarized.

Summaries for discrete variables will include frequencies and percentages. Percentages will be based on the number of subjects (eyes) with non-missing values. The denominator for percents will be the number of subjects (eyes) from the study population being analyzed. For each subject, baseline will be defined as the last non-missing measure prior to initiation of investigational treatment and endpoint will be defined as the measure of any follow-up scheduled visit. Change from baseline will be defined as (follow-up measure – baseline measure) and will be calculated if both baseline and follow-up endpoint are not missing.

The study eye will be the eligible eye with the highest total ocular surface fluorescein staining score at baseline or, if both eyes are eligible and have the same score, the study eye will be the right eye.

For each subject, the number of investigational eye drops used per day and for how many days during the course of study will be evaluated. It is expected that most subjects will not perform more than 6 applications per day on a continued regularly basis during the study.

The primary performance endpoint (mean change from baseline in total ocular surface fluorescein staining score) will be analyzed using analysis of covariance (ANCOVA) model. The model will include terms of treatment and baseline ocular surface staining score as covariates. Sensitivity analyses including investigator site as covariate will be performed. A 2-sided 95% confidence interval (CI) based on the ANCOVA model will be computed for the effect difference (CBL-102 Eye Drops *minus* Vismed® Multi). Non-

inferiority will be demonstrated if the upper bound of the 95% CI is less than 2 grades in the PP analysis. Supportive analysis of the primary endpoint will be performed on ITT population. The same ANCOVA model used to analyze the primary endpoint will be employed to analyze secondary continuous performance endpoints. Supportive analyses on secondary performance endpoints will be performed in the ITT and PP populations.

Ocular biomicroscopic assessment will be summarized at each visit using discrete summary statistics and presented by treatment.

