## 7.5 Primary performance endpoint analysis

The primary performance endpoint is the mean CFB in the study eye at visit 4 (D28  $\pm$  3 days) in ocular surface fluorescein staining score, combining corneal, nasal and temporal bulbar conjunctival fluorescein staining score, each graded from 0 to 5, according to the Oxford scheme.

The primary performance endpoint analysis will be performed on the per-protocol population.

The primary performance endpoint will be analyzed by an analysis of covariance including the treatment as fixed effect and the baseline ocular surface staining score as covariate (SAS® Mixed procedure). The two-sided 95% confidence interval for the difference [CBL-102 Eye Drops: D28-D0] – [Vismed Multi: D28-D0] will be computed by the model. The non-inferiority will be demonstrated if the upper bound of the 95% CI is less than 2.

In addition to this model, and depending on the results of the baseline characteristics description, other relevant baseline covariates could be added to the model.

A sensitivity analysis including investigator site as covariate will also be performed using the same model. Mean CFB by treatment and by center will be displayed (if necessary, small centers will be grouped).

Summary statistics for continuous variables will be presented for the total ocular surface fluorescein staining score at D0, D28, and for CFB at D28 for each treatment group.

This analysis will also be performed on patients from the ITT population.

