### 7.13.3 Performance endpoints analyses

#### 7.13.3.1 Quantitative data (including primary endpoint)

➤ Global effects

Analyzed variable Type 3 Tests of Fixed Effects				
Effect	Num DF	Den DF	F Value	Pr > F
Group				
Value at baseline				
Other covariable				

➤ Model estimates

Analyzed variable					
CBL-102 Eye Drops LSMeans		Vismed Multi LSMeans		CBL-102 Eye Drops – Vismed Multi Difference of LSMeans	
Estimate (+/-SE)	95% CI	Estimate (+/-SE)	95% CI	Estimate (+/-SE)	95% CI

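### The plan gives two possible baseline covariates for the secondary-endpoint ANCOVA: total staining score in the methods text, the analysed variable's own baseline in the table shell

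*SAP*

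**What the plan says.** **Covariate of the primary model.** SAP 7.5 specifies an analysis of covariance "including the treatment as fixed effect and the baseline ocular surface staining score as covariate". Protocol 7.6.1 agrees: "The model will include terms of treatment and baseline ocular surface staining score as covariates". The protocol synopsis names the same covariate.

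**Carry-over to secondary endpoints.** Protocol 7.6.1 states: "The same ANCOVA model used to analyze the primary endpoint will be employed to analyze secondary continuous performance endpoints". SAP 7.6 states: "The treatment groups will be compared at each post-baseline time using the same covariance model used to analyze the primary endpoint". Neither restates the covariate for each endpoint.

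**Text pointing to a different covariate.** In SAP 7.6 the multinomial sensitivity model is fitted "with the value at baseline as covariate". The shell in SAP 7.13.3.1 covers all quantitative performance endpoints, the primary included. Its effects table sits under a generic analysed-variable heading and has a covariate row labelled "Value at baseline". SAP 7.6 also tests a treatment-by-baseline interaction. If the interaction is kept, the treatment effect is evaluated at the overall mean of the D0 values. Neither statement names the variable.

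**Status.** SAP 7.6 describes the secondary tests as informational. SAP section 4, which lists departures from the protocol's statistical section, does not mention the covariate.

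**The concern.** One model has two descriptions. For the primary endpoint they coincide, because the value at baseline of the analysed variable is the baseline staining score. For TFBUT, Schirmer, the symptom sum score and the OSD-QoL dimensions they do not. A programmer working from the methods text would enter total staining at D0, and one working from the shell would enter the endpoint's own D0 value. For the three regional staining scores the methods text would adjust for the total, which contains the region's own grade but is not equal to it.

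The choice affects more than the point estimate. The interaction test, the D0 mean at which the effect is evaluated, and the residual normality check that can trigger a rank analysis all depend on which baseline is in the model. The two readings would give different estimates, intervals and p-values for most of the secondary results.

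**Working it through.** **1. The plan's own figure.** The documents give no figure for the secondary analyses. The arm size used below is the planned evaluable number. With one-sided alpha 2.5%, 90% power, margin 2, SD 2.5 and an assumed true difference of 0:

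n = 2 × 2.5² × (1.960 + 1.282)² / 2² = 32.8, so 33 per group, as stated.

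Allowing 20% for dropout plus violations, 33 / 0.80 = 41.25, so 42 per group and 84 in total, as stated. Nothing below changes these numbers.

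**2. Inputs that must be assumed.** The documents give no correlations or variances for the secondary endpoints. Let ρ be the correlation of an endpoint's baseline with its follow-up value, taken as 0.3, 0.5 and 0.7. Let k be the baseline SD divided by the follow-up SD. Take baseline staining as uncorrelated with the endpoint's change.

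**3. Residual variance of the change, in units of follow-up variance.**
- Own baseline as covariate: 1 − ρ²
- Total staining as covariate: 1 + k² − 2ρk

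The second exceeds the first by (k − ρ)², so the SE ratio is √[1 + (k − ρ)² / (1 − ρ²)]. With equal variances (k = 1) this reduces to √[2 / (1 + ρ)].

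| ρ | SE ratio, k = 1 | Equivalent n per arm, 33(1 + ρ)/2 | SE ratio, k = 0.7 |
|---|---|---|---|
| 0.3 | √1.538 = 1.24 | 21.5 | √(1.07/0.91) = 1.08 |
| 0.5 | √1.333 = 1.15 | 24.8 | √(0.79/0.75) = 1.03 |
| 0.7 | √1.176 = 1.08 | 28.1 | √(0.51/0.51) = 1.00 |

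The loss disappears where k = ρ and exceeds the k = 1 column when k is above 1.

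**4. Staining correlated with the endpoint.** At k = 1, let staining correlate r_b with the endpoint's baseline and r_f with its follow-up. The numerator becomes 2(1 − ρ) − (r_f − r_b)².
- For (r_b, r_f) = (−0.3, −0.2) the SE ratios are 1.24 / 1.15 / 1.08.
- For (0.3, 0.15) they are 1.23 / 1.14 / 1.06.

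A moderate correlation with staining changes little.

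**5. Bias, error rate and power by simulation.** 20,000 trials per setting, 33 per arm, k = 1, correlations −0.3 and −0.2 as above:

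| ρ | Mean SE, own / staining | Type I error, own / staining | Power at 0.7 SD, own / staining |
|---|---|---|---|
| 0.3 | 0.236 / 0.291 | 5.2% / 5.1% | 82% / 65% |
| 0.5 | 0.214 / 0.246 | 5.3% / 5.4% | 89% / 80% |
| 0.7 | 0.176 / 0.190 | 5.1% / 5.2% | 97% / 95% |

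Mean bias was within 0.003 SD of zero for both covariates. The 0.7 SD difference is an illustration and does not come from the plan.

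**6. Chance imbalance.** At k = 1, if the arms happen to differ by 0.2 SD in the endpoint's own baseline, the analysis without that baseline carries an error of size (1 − ρ) × 0.2 SD. That is 0.14 / 0.10 / 0.06 SD for ρ = 0.3 / 0.5 / 0.7. Own-baseline adjustment removes this error.

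**The case against.** The strongest reply is that the shell is also part of the written plan. It serves the primary and secondary endpoints together, and its baseline row, read under the analysed-variable heading, is the staining score for the primary endpoint and the endpoint's own baseline for the others. On that view, the same model means the same structure, and SAP 7.5 names staining only because staining is what it analyses. The generic interaction wording in SAP 7.6 and the absence of an entry in section 4 both fit this. The argument is good, and it is probably what was intended. It does not settle the matter, because the methods text names one covariate and no sentence says that it changes with the endpoint.

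A reader might infer that these endpoints will definitely be adjusted for the wrong baseline. The documents do not support that, since they contain both readings. A reader might also infer that regression to the mean would bias the comparison. In randomised arms it cancels on average, and the simulation shows no bias and a type I error near 5%.

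Three further limits stand:
- The 24% / 15% / 8% figures need equal variances. Entry requires TFBUT of 10 seconds or less (Protocol 2.2.1.1), so its baseline spread may be narrower than at follow-up, and the loss correspondingly smaller.
- For Visit 5 total staining, the named covariate already is the endpoint's own baseline.
- Instillation frequency is a listed secondary endpoint with no D0 value, so an own-baseline rule cannot apply to it.

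**Conclusion.** The covariate for the continuous secondary endpoints is stated inconsistently and should be settled. This is a conflict of wording, not an established wrong analysis. If the literal methods text were followed, TFBUT, Schirmer, symptom and OSD-QoL estimates would stay unbiased on average with valid tests. Their standard errors would be about 24% / 15% / 8% larger at ρ = 0.3 / 0.5 / 0.7, given equal variances and staining uncorrelated with the change, or about 8% / 3% / 0% at a baseline-to-follow-up SD ratio of 0.7. Chance imbalance in the endpoint's own baseline would go uncorrected. The correlations and SD ratios are assumptions throughout. No size is computed for the regional staining scores, which would be partly adjusted through the total.

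The primary non-inferiority conclusion, the sample size and Visit 5 total staining are unaffected, and no success claim rests on the secondary tests. Severity: minor.

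**What to change.** In SAP 7.6, replace the reference to the primary model with wording such as:

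*Analysis of covariance of change from baseline, with treatment as fixed effect and the D0 value of the variable being analysed as covariate, the same D0 value being used for the Treatment x Baseline test. Instillation frequency, which has no D0 value, is compared without a baseline covariate.*

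The exemption fits SAP 7.10.2, which already compares average daily administrations by a t test or Wilcoxon test. Record the clarification in SAP section 4 against Protocol 7.6.1.

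The cost is a short wording change before the treatment codes are broken. The D0 values are already collected, the shell already has the row, and neither the sample size nor the primary analysis changes.

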## 7.7 Safety analyses

All safety analyses for randomized subjects will be performed on the Safety population.

### 7.7.1 Bio-microscopic examination

Each sign will be described by treatment group and by eye (Studied eye and fellow eye) at each visit with an available data at the given visit. The worst grade observed during the study (Studied eye and fellow eye combined) will also be described by treatment group.

Data at the follow-up visits will be cross-tabulated with the data at baseline D0 and will be described in 6 classes: No change (no sign) / Disappearance / Improvement / No change (persistence of the sign) / Aggravation / Onset. If necessary, modalities will be pooled depending on the number of subjects.

### 7.7.2 Visual acuity

The visual acuity (decimal value) will be described for each eye (Studied eye and fellow eye) by treatment group at D28 and D90 by class:  $\geq 8/10$ ,  $<8/10$  and  $\geq 5/10$ ,  $< 5/10$  and  $\geq 1/10$ ,  $< 1/10$ .

Visual acuity decimal values will also be transformed into LogMar values for summary statistics at each time and on changes / baseline. They will be compared between the 2 groups at D28 and D90 (Student t-test for independent samples or a Wilcoxon rank-sum test if the data do not follow a normal distribution).

### 7.7.3 Device deficiency

ART device deficiency will be described at baseline. Deficiencies will be listed.

Investigational drops device deficiency will be described at each time after baseline. Deficiencies will be listed. If necessary, device deficiency rates will be compared between the 2 groups (chi-square test or a Fisher exact test depending on the sample size).

### 7.7.4 Adverse events

All adverse events variables, as described in the §3 “Safety variables” will be described and compared between groups (chi-square test or a Fisher exact test depending on the sample size).

All adverse events will be described in each treatment group by MedDRA’s « System Organ » and « Preferred Term ».

All adverse events will also be listed by group.

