1.0 OBJECTIVES

The primary objectives of this investigation are to show that the performance of CBL-102 Eye Drops is non-inferior to that of Vismed® Multi Eye Drops in subjects with moderate to severe keratoconjunctivitis sicca after 28 days, and to assess the safety of CBL-102 Eye Drops during a 90-day period with treatment administered 3 to 6 times per day.

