## 3 STUDY OVERVIEW

### 3.1 Objectives

The primary objectives of this investigation are to show that the performance of CBL-102 Eye Drops is non-inferior to that of Vismed® Multi eye drops in subjects with moderate to severe keratoconjunctivitis sicca after 28 days, and to assess the safety of CBL-102 Eye Drops during a 90-day period with treatment administered 3 to 6 times per day.

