### 6.3 Safety Variables

Topic	Area	Analyzed parameters	Time of evaluation
Bio-microscopic examination	Each eye	
 
- Eyelid Erythema
 
- Eyelid Swelling
 
- Ocular Discharge
 
- Conjunctival Chemosis
 
- Conjunctival Hyperemia
 
- Corneal Erosion
 
- Corneal Edema
 
- Corneal Infiltrates
 
	D0 / D28 / D90
Visual acuity test	Each eye	
 
- LogMAR = -Log(Visual acuity decimal)
 
	D0 / D28 / D90
Adverse events	All body	
 
- At least one AE during the study
 
- At least one TEAE during the study
 
- At least one ADE during the study
 
- At least one serious AE during the study
 
- At least one serious TEAE during the study
 
- At least one serious ADE during the study
 
- At least one unanticipated serious ADE during the study
 
- At least one anticipated serious ADE during the study
 
	During all study
Adverse events	Ocular	
 
- At least one ocular AE during the study
 
- At least one ocular TEAE during the study
 
- At least one ocular ADE during the study
 
- At least one ocular TEAE related (possible, probable, certain) to the eye drops during the study
 
- At least one ocular TEAE related (possible, probable, certain) to the procedure during the study
 
- At least one serious ocular AE during the study
 
- At least one serious ocular TEAE during the study
 
- At least one serious ocular ADE during the study
 
- At least one unanticipated serious ocular ADE during the study
 
- At least one anticipated serious ocular ADE during the study
 
- Ocular AE description
 
	During all study

Topic	Area	Analyzed parameters	Time of evaluation

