Adverse events	Non-ocular	
 
- At least one non-ocular AE during the study
 
- At least one non-ocular TEAE during the study
 
- At least one non-ocular ADE during the study
 
- At least one non-ocular TEAE related (possible, probable, certain) to the eye drops during the study
 
- At least one non-ocular TEAE related (possible, probable, certain) to the procedure during the study
 
- At least one serious non-ocular AE during the study
 
- At least one serious non-ocular TEAE during the study
 
- At least one serious non-ocular ADE during the study
 
- At least one unanticipated serious non-ocular ADE during the study
 
- At least one anticipated serious non-ocular ADE during the study
 
- Non-ocular AE description
 
	During all study
Device Deficiency (ART)	-	
 
- At least one DD
 
- DD description
 
	Before D0
Device Deficiency (Investigational product)	-	
 
- At least one DD
 
- DD description
 
	After D0

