### 7.2 General approach

Quantitative variables will be summarized into count of non-missing data, mean, standard deviation, minimum, maximum, median and, if necessary, 95% confidence interval of the mean.

Categorical data will be described into count and percentage with 95% confidence interval if necessary.

All statistical analyses will be performed at the 5% significance level using 2-sided test or 2-sided confidence intervals if necessary.

Normality will be tested by the Shapiro-Wilk at the 1% threshold.

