#### 7.13.4 Adverse events table

System-Organ	Preferred Term	CBL-102 Eye Drops		Vismed Multi		Total	
		n	% / N patients	n	% / N patients	n	% / N patients
System-Organ 1	PT 1						
	PT 2						
	PT x						
	TOTAL						
System-Organ 2	PT 1						
	PT 2						
	PT x						
	TOTAL						
System-Organ x	PT 1						
	PT 2						
	PT x						
	TOTAL						

n = Number of patients with at least the AE once.

N = Total number of patients

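### Adverse events are compared between arms only by chi-square or Fisher tests on 28 yes/no rows, and no risk difference with a confidence interval is planned

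*SAP*

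**What the plan says.** Protocol section 1.0 names two primary objectives. One is non-inferiority on staining at Day 28. The other is "to assess the safety of CBL-102 Eye Drops during a 90-day period", and SAP 3.1 repeats it. No hypothesis, margin or power is attached to safety. The sample size (Protocol 7.3, SAP 3.6) rests on the staining endpoint alone.

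SAP 7.7.4 states that all the adverse-event variables "will be described and compared between groups (chi-square test or a Fisher exact test depending on the sample size". The variables are in SAP 6.3: 8 all-body rows (for example "At least one TEAE during the study"), 10 ocular rows and 10 non-ocular rows (for example "At least one non-ocular AE during the study"). That makes 28 yes/no rows, leaving aside the two rows that are event descriptions.

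The general rule is in SAP 7.2: "All statistical analyses will be performed at the 5% significance level using 2-sided test or 2-sided confidence intervals if necessary". For percentages the same section says: "Categorical data will be described into count and percentage with 95% confidence interval if necessary". That provides for an interval around a percentage, at discretion. It does not provide for an interval around the difference between arms. No multiplicity rule is given for the adverse-event rows.

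SAP 7.6, 7.8 and 7.10 each state that their tests are informational only. SAP 7.7 carries no such statement.

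**The concern.** For a safety objective in a comparative trial, the useful question is how much more often events could occur on CBL-102 than on Vismed Multi, given the data. A test of equality does not answer it. With about 42 subjects per arm, a non-significant result is compatible both with no difference and with a clinically relevant excess, and a p-value alone does not show which values remain open. The report would then hold counts, percentages and p-values for a primary objective, with no planned statement of the size of difference that the data exclude. The missing informational label adds to this: as written, the adverse-event tests carry less caution than the tests on secondary endpoints.

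**Working it through.** **Subjects per arm.** The plan's own figure comes first. With margin 2, SD 2.5, one-sided alpha 2.5% and 90% power:

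n = 2 × [(1.960 + 1.282) × 2.5 / 2]² = 32.8, rounded up to 33 per arm, as stated.

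Allowing 10% dropout plus 10% violations: 33 / 0.80 = 41.25, rounded up to 42 per arm, or 84 in total, as stated. The Safety population is all treated subjects, so it has at most about 42 per arm.

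**Power of the planned tests.** The documents give no adverse-event rates, so all rates here are illustrative assumptions. Power is exact: sum over every pair of counts (a, b) the product Bin(a; 42, p1) × Bin(b; 42, p2) wherever the two-sided p is below 0.05. SAP 7.7.4 gives no cut-off for choosing between the tests, so two versions are shown: Fisher throughout, and uncorrected chi-square with Fisher when an expected count is below 5.

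| Vismed Multi rate | CBL-102 rate | Fisher | Chi-square or Fisher |
|---|---|---|---|
| 5% | 10% | 5% | 6% |
| 10% | 20% | 18% | 24% |
| 5% | 15% | 20% | 25% |
| 10% | 25% | 36% | 45% |
| 5% | 20% | 44% | 52% |
| 20% | 40% | 44% | 52% |
| 10% | 30% | 56% | 66% |
| 5% | 25% | 68% | 75% |
| 5% | 30% | 85% | 89% |

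Excesses of 10 points are usually missed. Excesses of 15 points are missed somewhat more often than not, or about as often as not, depending on the base rate and the test. Excesses of 20 points or more from base rates of 5% to 10% are detected at least 56% of the time.

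**What an interval would add.** Take 6/42 on CBL-102 against 2/42 on Vismed Multi. The smallest expected count is (6 + 2) / 2 = 4, so the usual rule selects Fisher, which gives p = 0.26.

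- Difference: 14.3% − 4.8% = +9.5 points.
- Wilson 95% limits: 6.7% to 27.8% for 6/42, and 1.3% to 15.8% for 2/42.
- Newcombe lower limit: 9.5 − √[(14.3 − 6.7)² + (15.8 − 4.8)²] = −3.9 points.
- Newcombe upper limit: 9.5 + √[(27.8 − 14.3)² + (4.8 − 1.3)²] = +23.5 points.

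(The limits were computed from unrounded values.) A second case, 9/42 against 4/42, gives Fisher p = 0.23, a difference of +11.9 points and an interval from −4.0 to +27.5.

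**Zero counts.** With 0/42 events, the exact two-sided 95% upper limit is 1 − 0.025^(1/42) = 8.4%.

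**The case against.** Several points on the other side are sound, and they limit how far the concern goes.

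- **Not all safety data are affected.** A reader might infer that safety as a whole is compared only by these tests. It is not. Visual acuity, a named safety endpoint, is compared by t-test or Wilcoxon (SAP 7.7.2). Biomicroscopy is described by worst grade and by shift from baseline (SAP 7.7.1). Adverse events are also tabulated by System Organ and Preferred Term and listed in full.
- **Large excesses are not usually missed.** A reader might infer this from the small sample, but the table above contradicts it for excesses of 20 points or more from base rates of 5% to 10%. A case such as 8/42 against 2/42 also does not show a hidden excess. Its smallest expected count is exactly 5, so the usual rule selects chi-square with p = 0.043 (Fisher gives 0.088), and the Newcombe interval just excludes zero.
- **Chance positives are a weak argument.** For 28 independent tests at exactly 5%, the chance of at least one false positive would be 1 − 0.95^28 = 76%. The rows are nested, however, and Fisher's actual size at 42 per arm is about 0.5% at a 5% event rate and 1.8% at 10%.
- **The plan does not misread its tests.** Neither document says that a non-significant result will be taken as evidence of safety, and the objective is only to assess safety.
- **The raw counts will be available.** A reader of the report could compute a risk difference. The template in SAP 7.13.4 ("n = Number of patients with at least the AE once") is for the System Organ and Preferred Term table, so its lack of an interval column proves little about the 28 summary rows.

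What remains is that the only between-arm method specified for the adverse-event rows is a test of equality. Leaving readers to compute the interval does not replace specifying it in advance for a primary objective.

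**Conclusion.** The point holds for adverse events, as a gap in the planned reporting. Under the assumed rates and 42 per arm, a doubling from 10% to 20% would fail to reach p<0.05 about 76% to 82% of the time, and a rise from 5% to 15% about 75% to 80% of the time. Non-significant results such as 6/42 against 2/42 or 9/42 against 4/42 leave an excess of roughly 23 to 28 points open, and nothing planned would display that. The power figures depend on event rates that the documents do not supply and, to a lesser degree, on which test is chosen. The absence of a planned interval for the difference depends on neither. The primary non-inferiority conclusion on staining is unaffected. This is a low-cost improvement that should be made, not a flaw that invalidates the safety analysis.

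**What to change.** In SAP 7.7.4, add the risk difference (CBL-102 minus Vismed Multi) with a 95% Newcombe confidence interval for four rows: any TEAE, any ocular TEAE, any related ocular TEAE and any serious TEAE. SAP 6.3 separates relation to the eye drops from relation to the procedure, so the table should say which is meant. Where a count is zero, give the exact upper limit for that arm. State that the adverse-event tests are informational only, in line with SAP 7.6, 7.8 and 7.10. The p-values may stay; removing them would be a matter of preference. In the same edit, correct the cross-reference in SAP 7.7.4, which points to section 3 although the safety variables are in 6.3.

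The cost is SAP wording and a few table columns, with no new data. The downside is that wide intervals will be shown openly.
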